method combining mechanical and chemical debridement with 1.7% HP gel . The HP gel is directed into periodontal pockets via a custom tray, as an aid to manage biofilms better for patients with gingivitis and periodontitis. The FDA approved  $\leq 3\%$  HP gel as an oral debriding agent and an oral wound cleanser. The FDA also cleared the prescription tray branded as the Perio Tray® (Perio Protect, St. Louis, MO) as a subgingival delivery medical device in 2004 (21 C.F.R. § 872.6870). Customized extensions of the tray support the customized seal to direct the gel deep down into the sulcus or periodontal pocket and overcome the crevicular fluid flow .

Custom tray application of the HP gel as an adjunct to SRP in the treatment of chronic periodontitis has been investigated. In randomized controlled studies, it was demonstrated that significant reduction of probing depth (PD) and bleeding without mechanical intervention were seen after two weeks of HP prescription tray regimen followed by SRP and the results were maintained for up to six months with the daily use of HP prescription trays for 10 weeks . The prescription tray delivery of HP gel as an adjunctive to SRP was effective before and after full-mouth SRP in reducing PD about 1mm over SRP alone for six months in chronic periodontitis patients . However, there is currently no randomized control clinical study evaluating the differences in the duration effects of the treatment in chronic periodontitis patients with customized delivery of hydrogen peroxide gel.

The primary objectives of this randomized, controlled, single-blind, parallel clinical study are: (1) to examine if the prescription tray delivery of HP gel adjunctive to SRP results in a greater clinical improvement than SRP alone over a six-month period; and (2) to

evaluate whether the custom tray delivery of the HP gel can decrease inflammation prior to SRP.

The secondary objective is to compare if there is a difference between the length of treatment of adjunctive HP gel (3-months versus 6-months). It is hypothesized that adjunctive HP therapy will provide additional clinical benefits in PD reduction, attachment gain, and reduction of bleeding on probing (BOP) compared to SRP alone.

Null Hypotheses:

There is no significant difference between the treatment groups (SRP + HP13 vs. SRP + HP26 vs. SRP alone) with regards to reduction in PD.

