### **Treatment Phase**

The treatment phase began with non-surgical periodontal treatment. The two therapy test groups will have used their customized application HP gel for four weeks prior to the start of treatment. Non-surgical periodontal treatment consisted of 1-, or 2-visit SRP using ultrasonic and hand instrumentation with local anesthesia. Surfaces were to be deemed clean and debrided when subgingival deposits cannot be tactiley detected and the root surface feels smooth to the operator. Re-evaluation of SRP was done 8 weeks after the last session of SRP, at week 13. One therapy test group stopped using the HP

therapy at the re-evaluation visit (HP13). Whereas the other test therapy group received impressions for a new customized tray to continue application of HP therapy for an additional 13 weeks (HP26) to the termination of the study.

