### **Custom HP Tray Application**

The principal investigator supervised first use of trays and HP gel and, if needed, adjustment were made to trays so that it seated completely and comfortably in the subject's mouth while maintaining an adequate seal. Each subject applied a thin ribbon of gel throughout tooth indentations to provide a dosage of ~0.75 gram in each tray using a mass scale. Treatment frequency will be fixed throughout the study duration: Start of Treatment (Visit 2, Week 0) to 8-weeks following SRP (Visit 5, Week 13): two treatments per day, 15 minutes each

Subjects in the treatment groups documented tooth brushing and the gel tray applications in calendar journals for the entire duration of the study. Subject compliance was estimated throughout the study by reviewing diaries and by massing gel tubes at each visit. Patients were instructed to bring in their treatment tubes to each visit.

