## **Study Schedule**

A study schedule summary follows for HP group arms:

- Visit 1: Screening, recruitment, randomization and periodontal consultation was completed. PVS impressions were taken for fabrication of both prescription trays and customized stents created for clinical measurements if patient accepts and were recruited as subjects.
- Visit 2, Week 0: Data collected for clinical measurements with custom stents for RAL, PD and R-rec (Baseline). Delivery of prescription tray and first supervised instructions and placement of the gel for the treatment groups. OHI.
- Visit 3, Week 4: 4 weeks after the delivery of the tray and the gel; data collection of periodontal parameters with stent, 2 quadrants of SRP, reinforcement of OHI. Inquire if subjects had any adverse events with the use of hydrogen peroxide gel
- Visit 4, Week 5: No more than 1-week elapsed time since visit 4; SRP of 2 remaining quadrants, reinforcement of OHI.

- Visit 5, Week 13: Periodontal re-evaluation 8 weeks after last quadrant of SRP; data collection of periodontal parameters with stent, SRP on residual sites with detectable calculus, termination of peroxide use in HP13. For subjects enrolled in HP26 , new impressions were made for new prescription tray.
- (Visit 6, Week 14 [HP26 only]): New prescription tray delivery
- Visit 6, Week 17: Periodontal maintenance, reinforcement of OHI.
- Visit 7, Week 26: Data collection of periodontal parameters with stent (final exam), periodontal maintenance, reinforcement of OHI.

A study schedule summary follows for SRP arm:

- Visit 1: Screening, recruitment, and randomization. Data collection of periodontal parameters by residents and verified by attending periodontists. PVS impressions will be taken for fabricating of customized stents for clinical measurements if patient accept and are recruited as subjects.
- Visit 2, Week 0: Clinical measurements with stents (Baseline).
- Visit 3, Week 4: SRP and OHI
- Visit 3, Week 5: Remaining quadrants of SRP, reinforcement of OHI
- Visit 4, Week 13: Periodontal re-evaluation 8 weeks after last quadrant of SRP; data collection of periodontal parameters with stent, SRP on residual sites with detectable calculus, reinforcement of OHI
- Visit 5, Week 17: Periodontal maintenance, reinforcement of OHI
- Visit 6, Week 26: Data collection of periodontal parameters with stent, periodontal maintenance, reinforcement of OHI.

[figure not shown]

Figure 1. CONSORT Flow Diagram

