## **Statistical Analysis**

The primary outcome variables are PD reduction, RAL gain, and reduction in BOP. PD data was computed to provide a mean score per mouth. Secondary efficacy variables were BOP, and MQH. BOP was computed to provide a mean score per mouth for each clinical assessment and were analyzed using repeated measures (ANOVA). Outcome variable data analysis consisted of between-treatment and within-treatment (longitudinal) comparisons of PD and CAL at all examination time points using parametric procedures. Between-treatment and within-treatment comparisons employed baseline data and analysis of covariance (ANCOVA) for follow-up data. All comparisons were performed using two-sided hypothesis tests, and employed a 0.05 level of significance.

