Figures 4, 5, 6, and 7 show baseline, 4-week, re-evaluation, and final MQH plaque scores. Plaque scores varied throughout the four timepoints with no obvious differences between groups.

[figure not shown]

Figure 5. Baseline MQH scores for A) SRP, B) HP13, and C) HP26

[figure not shown]

Figure 6. 4-Week MQH scores for A) SRP, B) HP13, and C) HP26.

[figure not shown]

Figure 7. Re-Evaluation MQH scores for A) SRP, B) HP13, and C) HP26.

[figure not shown]

Figure 8. Final MQH scores for A) SRP, B) HP13, and C) HP26.

[figure not shown]

Figure 9. Mean BOP in each group, SRP, HP13, and HP26

[figure not shown]

Figure 10. BOP % in pockets initially <5 mm

[figure not shown]

Figure 11. BOP % in pockets initially  $\geq 5$ mm

Figure 8 shows mean BOP. Baseline mean BOP was 45% for SRP, 57% for HP13, and 63.1% for HP26. At 4-weeks, mean BOP was 45% for SRP, 60% for HP13, and 44% for HP26. At re-evaluation, mean BOP was 37% for SRP, 30% for HP13, and 27% for HP26. Final mean BOP scores were 44% for SRP, 33% for HP13, and 28% for HP13. Mean BOP was significantly reduced in all groups between 4-week examination and re-evaluation with mean BOP scores at final examination staying similar to levels at re-evaluation for HP13 and HP26 groups. Mean BOP scores at final examination group for SRP group was similar to baseline.

Figure 9 shows BOP % in pockets initially  $< 5$ mm. At baseline, 24% of pockets  $< 5$ mm were BOP for SRP, 47% for HP13, and 52% for HP26. At 4-week examination BOP % were 29% for SRP, 44% for HP13, and 35% for HP26. At re-evaluation, BOP %

was 27% for SRP, 21% for HP13, and 22% for HP26. At the final exam, BOP % was 33% for SRP, 26% for HP13, and 22% for HP26.

Figure 10 shows BOP % in pockets initially  $\geq 5$ mm. At baseline, BOP % was 92% for SRP, 81% for HP13, and 91% for HP26. At 4-week examination, BOP % was 91% for SRP, 93% for HP13, and 83% for HP26. Re-evaluation BOP % was 91% for SRP, 78% for HP13, and 75% for HP26. At final examination, BOP % was 88% for SRP, 79% for HP13, and 78% for HP26.

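### The 3- versus 6-month gel comparison has no contrast anchored at week 13, when the two gel arms first differ

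*Combined protocol and SAP*

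**What the plan says.** The Introduction sets the duration question as an objective of its own: "The secondary objective is to compare if there is a difference between the length of treatment of adjunctive HP gel (3-months versus 6-months". It adds that no randomized trial has yet addressed it.

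Up to the re-evaluation visit the two gel arms are treated alike. Custom HP Tray Application fixes the frequency from week 0 to week 13 at "two treatments per day, 15 minutes each". The arms separate at week 13, as Treatment Phase states: "One therapy test group stopped using the HP". The other arm continues to week 26. The Study Schedule for the gel arms places a stent examination at that week-13 visit, listed ahead of residual SRP and of the end of gel use in HP13. HP26 alone then has an added step: "Visit 6, Week 14 [HP26 only]): New prescription tray delivery".

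Baseline is the week-0 visit: "Data collected for clinical measurements with custom stents for RAL, PD and R-rec (Baseline". For analysis, the Statistical Analysis section plans "comparisons of PD and CAL at all examination time points using parametric procedures" and then states "Between-treatment and within-treatment comparisons employed baseline data and analysis of covariance (ANCOVA) for follow-up data". BOP is assigned to repeated measures ANOVA in that section, while the Abstract lists it under ANCOVA. No separate model, covariate or contrast is given for HP13 versus HP26.

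**The concern.** For the duration question, weeks 0 to 13 are a shared run-in. Any difference between HP13 and HP26 over that period cannot come from length of use. A week-26 comparison adjusted only to week 0 still contains it. The week-13 examination is the natural reference: it falls where the regimens part, is already collected, and probably predicts week 26 better than week 0 does. The plan makes no between-arm use of it for this objective.

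At stake is how precisely the trial can answer its own secondary question, and how far the estimate depends on where the two arms happened to stand at week 13. Results, Discussion and Conclusion contain no readable HP13-versus-HP26 estimate or test and no answer on duration.

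**Working it through.** There is no stated power or duration-effect figure to reproduce. The plan gives only three groups of 20. Weeks are counted as in the Study Schedule, and CAL is read as RAL.

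**1. Inputs (Results chapter).** In "Final mean BOP scores were 44% for SRP, 33% for HP13, and 28% for HP13" the second HP13 is read as HP26.

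| Outcome | Arm | Week 0 | Week 13 | Week 26 |
|---|---|---|---|---|
| BOP, % | HP13 | 57 | 30 | 33 |
| BOP, % | HP26 | 63.1 | 27 | 28 |
| PD, mm | HP13 | 4.11 | 3.43 | 3.40 |
| PD, mm | HP26 | 3.83 | 3.14 | 3.23 |
| RAL, mm | HP13 | 6.97 | 6.15 | 6.71 |
| RAL, mm | HP26 | 7.04 | 6.39 | 6.53 |

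**2. Split of the difference.** Let D be HP13 minus HP26, so that a positive value favours HP26. The difference in change over weeks 0-26 is D26 − D0 = (D13 − D0) + (D26 − D13).

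- BOP: D = −6.1, 3, 5. Total 5 + 6.1 = 11.1 points; before divergence 3 + 6.1 = 9.1 (82%); after it 5 − 3 = 2.0.
- PD: D = 0.28, 0.29, 0.17. Total −0.11 mm; before 0.01; after −0.12.
- RAL as printed: D = −0.07, −0.24, 0.18. Total 0.25 mm; before −0.17; after 0.42.

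**3. Check on RAL.** By the definitions in Clinical Periodontal Parameters, PD + R-Rec should equal RAL. This agrees within 0.04 mm in every arm at weeks 0, 4 and 13 (reading the duplicated HP13 label in the baseline R-Rec sentence as HP26), with one exception: HP13 at week 13, 3.43 + 3.27 = 6.70 against a printed 6.15. With 6.70, D13 = 0.31 and the split becomes 0.25 = 0.38 + (−0.13), so the post-divergence sign reverses.

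**4. ANCOVA instead of change scores.** The adjusted difference is D26 − b·D0 or D26 − b·D13, where the common slope b is unknown and is run from 0 to 1.

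- BOP: 5.0 to 11.1 points adjusted to week 0; 5.0 to 2.0 adjusted to week 13.
- PD: 0.17 to −0.11 mm against 0.17 to −0.12 mm. The two references agree within 0.01 mm at any slope.

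**5. Bias.** Data were simulated with no duration effect (8,000 runs; 20/20 and 3/9 patients; assumed correlations 0.5-0.7 for weeks 0 and 13, 0.4-0.6 for weeks 0 and 26, 0.8-0.9 for weeks 13 and 26). Week-0 ANCOVA had a mean estimate within 0.01 SD of zero and type I error of 0.047 to 0.054. Its estimate correlated 0.68 to 0.84 with the week-13 difference. The 3/9 runs assume that loss of patients is unrelated to outcome.

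**6. Precision.** The documents give no correlations. Assume 0.4-0.5 between weeks 0 and 26 (r0) and 0.6-0.8 between weeks 13 and 26 (r13). The residual variance ratio is (1 − r13²)/(1 − r0²).

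- Least gain: 0.64/0.75 = 0.85, a 15% cut.
- Most gain: 0.36/0.84 = 0.43, a 57% cut.

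The detectable difference at 80% power is (1.96 + 0.84)·√[(1 − r²)(1/n1 + 1/n2)] in SD units.

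- 20 per arm: 0.77-0.81 with week 0; 0.53-0.71 with week 13.
- 3 versus 9: 1.62-1.71 with week 0; 1.12-1.49 with week 13. The normal quantiles flatter so small a sample.

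**The case against.** Allocation took place at enrolment, so the week-26 difference adjusted to week 0 is a legitimate randomized estimate of assignment to 3 versus 6 months. That stands. A reader might infer that the plan builds in bias or inflates false positives; with all randomized patients analysed it does neither.

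A reader might also infer that the printed data give the wrong answer on duration. They do not show that. No duration effect is reported, so nothing has been misattributed. For PD the choice of reference hardly matters. For mean BOP the size changes but the direction does not: both references favour HP26. The split also varies by pocket depth: in pockets initially under 5 mm, 5 of 9 points arise after week 13; in those of 5 mm or more, 13 arise before and −2 after.

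BOP, the clearest example, may not fall under the ANCOVA sentence. This is true on the Statistical Analysis text, but repeated measures ANOVA over four visits does not isolate weeks 13 to 26 either unless a contrast is named. Results do say that BOP stayed near its re-evaluation level in both gel arms, but that is a statement within each arm and not a comparison between them.

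Finally, week 13 comes after randomization. That is no bar here, because assigned duration has not acted by then, provided that knowing the assigned duration does not alter earlier gel use.

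**Conclusion.** The point holds as a gap in specification and efficiency. The duration objective has no named contrast, and the one measurement taken where the arms part is not used as its reference. Week-0 adjustment is valid under intact randomization but less precise: residual variance could fall by about 15% to 57% with week 13 as covariate, under the assumed correlations. The BOP means show a realised estimate that largely follows a gap present before divergence (9.1 of 11.1 points, on the reading of the label above). They do not show a design bias. PD is practically unaffected, and RAL is undecided until 6.15 and 6.70 mm are reconciled.

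Two limits apply. Results report 3 HP13 and 9 HP26 completers against 20 planned per group, so in that subset randomization no longer assures that week-13 gaps are chance. And because HP26 alone gets a re-made tray and an extra visit, the contrast is not length of use alone.

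**What to change.** Add to the Statistical Analysis section, for the secondary objective:

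- One per-patient contrast, HP26 versus HP13 at week 26, for PD, RAL and BOP, by ANCOVA with the week-13 value of the same outcome (taken before residual SRP) and the week-0 value as covariates, in all randomized gel patients with available data.
- Week-0 adjustment kept for gel versus SRP.
- HP13 versus HP26 at weeks 4 and 13 reported as a comparability check and not as a duration result.
- The contrast described as stopping at week 13 versus continuing with a re-made tray to week 26.

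Before the re-run, reconcile HP13's week-13 RAL and correct the duplicated arm labels.

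The cost is a few sentences and a re-analysis of data already collected. Patients without a week-13 examination need a mixed model or their baseline value. With 12 gel completers, two covariates leave 12 − 4 = 8 residual degrees of freedom, so report the estimate with its confidence interval and say plainly that it is very imprecise.

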## ABSTRACT OF THE THESIS

Custom Application of Peroxide Gel as Adjunct to Scaling/Root planning in Treatment of Periodontitis

by

[name]

Master of Science, Graduate Program in Periodontics

Loma Linda University, September 2019

[name] [name], Chairperson

**Aim:** This study was aimed to evaluate and compare the clinical effects of scaling and root planning (SRP) combined with local delivery of 1.7% HP in customized trays to that of SRP alone.

**Materials and Methods:** Sixty patients with generalized moderate to chronic severe periodontitis will be assigned to three groups treated by SRP plus HP gel with a custom prescription tray application. The test groups will receive twice daily 1.7% HP gel in custom trays four weeks prior to SRP and will continue to application for up to 3- and 6-months post-SRP. Baseline data that is collected at the start of the study will be collected again at 4, 13, and 26 weeks post-SRP and analyzed for any changes and thus main outcome variables will include changes in pocket depth (PD), relative recession (R-Rec), relative attachment level (RAL), and changes in bleeding (BOP) using ANCOVA of main effects.

**Results:** Repeated measure ANOVA showed significant difference in pocket depth among all time points in all treatment groups. Mean BOP was significantly reduced in all groups between 4-week examination and re-evaluation with mean BOP scores at final

examination staying similar to levels at re-evaluation for HP13 and HP26 groups. Mean BOP scores at final examination group for SRP group was similar to baseline.

**Discussion:** The use of adjunctive HP in custom fabricated trays presents with no adverse effects. Significant improvement was evident in pocket depth and attachment level in both treatment groups between after 4 weeks of using the tray. No significant effect found in SRP group between baseline and 4 weeks. After SRP, significant difference was seen in all three groups between 4 weeks and 3 months.

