## **Exclusion Criteria**

- 1) Any systemic conditions or medication intake that can alter periodontal status (e.g. uncontrolled diabetes (with <3-month recent HbA1c of  $>8.5\%$ ), anti-seizure medication, immunosuppressant, and calcium channel blockers with clinical sign of gingival overgrowth.
- 2) Immune-compromised state.

- 3) Any current heavy smoking habits (>10 cigarettes/day)
- 4) Any medical condition or history requiring prophylactic antibiotic coverage prior to dental treatment.
- 5) Females who are lactating or pregnant (as determined by medical history) or planning to become pregnant for the duration of the study.
- 7) Physical limitations/restrictions compromising oral hygiene procedures.
- 8) The presence of significant oral soft tissue pathology and/or lesions associated with ill-fitting appliances or restorations.
- 9) Tooth mobility associated with advanced periodontal disease (e.g. score of >2 using Miller Classification).
- 10) Any temporomandibular joint disorders.
- 11) Grossly carious, orthodontically banded, and third molars will not be included in the tooth count.
- 12) Presence of any significantly tipped, crowded, or largely defective restorations.
- 13) Any extreme adverse events relating to the use of HP gel (e.g. prolonged tooth hypersensitivity or aberrant soft tissue/mucosal reaction)

All participants were screened and evaluated at Loma Linda University School of Dentistry Graduate Periodontics Department. There are three groups of 20 patients, two therapy test groups and the control group.

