## CHAPTER FOUR

### DISCUSSION

This randomized, examiner-blind, parallel-design, clinical trial compared the effectiveness of SRP to daily treatment with 1.7% hydrogen peroxide using prescription, custom-fabricated dental trays as an adjunct to SRP. The results of this study demonstrate that the peroxide/prescription tray treatment regimen in combination with SRP is statistically significant in terms of reduction of BoP

In contrast to prior studies (Putt 2012, 2013 Journal of Clinical Dentistry), this study did not provide evidence to show that the use of peroxide/prescription tray regimen prior to SRP would reduce pocket depths without mechanical intervention. According to Putt 2012, the mean difference between test and control group after two weeks of 4-times daily use hydrogen peroxide was 0.44 mm in sites >5mm. The difference between test and control groups for all sites was 0.18mm. The difference that was seen between our study was that the subjects were instructed to use twice daily hydrogen peroxide, therefore the total “contact time” of peroxide is effective half.

The amount of marginal tissue recession over time did not demonstrate an increase of soft tissue recession over time with the use of the prescription trays indicated that the physical seal along the gingival margin does not induce or propagate recession.

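### Three primary outcomes are each tested at 0.05 with no multiplicity rule, decisive visit or rule for success, and BOP is listed as both primary and secondary

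*Combined protocol and SAP*

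**What the plan says.** The Statistical Analysis section opens with "The primary outcome variables are PD reduction, RAL gain, and reduction in BOP". Two sentences later it says "Secondary efficacy variables were BOP, and MQH". BOP therefore appears in both lists.

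The planned analyses differ by outcome. For BOP: "BOP was computed to provide a mean score per mouth for each clinical assessment and were analyzed using repeated measures (ANOVA)". For pocket depth and attachment level, the plan makes between- and within-treatment "comparisons of PD and CAL at all examination time points using parametric procedures". CAL is not defined, and I take it to mean the RAL outcome. The threshold is the same throughout: "All comparisons were performed using two-sided hypothesis tests, and employed a 0.05 level of significance".

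Chapter One has two primary objectives: clinical improvement over SRP alone across six months, and reduced inflammation before SRP. The secondary objective compares the two gel durations. Chapter One also states one three-group null hypothesis each for PD, attachment gain and BOP. The planned size is given under Exclusion Criteria: "There are three groups of 20 patients, two therapy test groups and the control group". The Abstract says that data "will be collected again at 4, 13, and 26 weeks post-SRP".

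No section gives an adjustment, a testing order, a single primary visit, or a statement of whether one, some or all of the primaries must succeed. The Discussion then concludes that the gel regimen "in combination with SRP is statistically significant in terms of reduction of BoP".

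**The concern.** With three primaries and no rule joining them, a significant result on any one can be presented as the trial's success. The 0.05 level then describes a single test and not the conclusion drawn from the set. The double listing of BOP makes this worse, because BOP is the outcome on which the Discussion bases its claim for the regimen. A reader cannot tell from the plan whether that claim is a primary finding, a secondary one, or the best of several.

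**Working it through.** **Inputs from the documents.** Two-sided 0.05 per comparison; 3 primary outcomes; 3 arms, 20 planned in each; 3 follow-up assessments; 15 completers (SRP 3, HP13 3, HP26 9; Results). The 0.05 is a per-test setting. No family-wise level, power or sample-size derivation is given, so there is no figure of the plan's to reproduce.

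**Assumed, not in the documents.** Correlations of 0 to 0.8 between outcomes and 0 to 0.8 between visits.

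**Step 1: narrowest reading.** One three-group test per outcome at one visit gives 3 tests.
- If independent: 1 − 0.95³ = 1 − 0.8574 = 0.143.
- Upper bound under any dependence: 3 × 0.05 = 0.15.

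**Step 2: all three follow-up visits for all three outcomes.** This gives 3 × 3 = 9 tests.
- If independent: 1 − 0.95⁹ = 0.370.
- Upper bound: 9 × 0.05 = 0.45.

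**Step 3: allow for correlation.** Normal data were simulated with no true differences, using three-arm F-tests at 0.05 and 20,000 runs per row. Entries are the chance of at least one false positive.

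| Outcome / visit correlation | 3 tests, 20/20/20 | 3 tests, 3/3/9 | 9 tests, 20/20/20 | 9 tests, 3/3/9 |
|---|---|---|---|---|
| 0 / 0 | 14.2% | 14.6% | 36.9% | 37.3% |
| 0.3 / 0.5 | 13.7% | 13.7% | 32.2% | 33.0% |
| 0.5 / 0.5 | 13.4% | 12.9% | 31.0% | 30.8% |
| 0.5 / 0.7 | 12.6% | 13.1% | 26.7% | 27.9% |
| 0.8 / 0.8 | 10.5% | 10.3% | 19.8% | 20.3% |

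The simulation error near 14% is √(0.143 × 0.857 / 20,000) = 0.25 percentage points, so the 14.6% is consistent with the exact 14.3%.

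**Step 4: effect of Holm.** Order the three p-values and compare them in turn with 0.05/3 = 0.0167, 0.05/2 = 0.025 and 0.05, stopping at the first failure. A further run with the same settings gave a family-wise rate of 3.6–5.0% for the three tests at one visit.

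**Step 5: what supports the BOP claim.** The Results text reports a significant fall in mean BOP from week 4 to re-evaluation in all groups: SRP 45% to 37% (8 points), HP13 60% to 30% (30 points), HP26 44% to 27% (17 points). That is a within-arm result, and it includes the arm without gel. No between-group BOP test or p-value appears in the text.

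**The case against.** Several points on the other side have force.

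- **The double listing may be a drafting slip.** The Abstract, the hypothesis and null in Chapter One, and the first sentence of Statistical Analysis all treat BOP as a main or primary outcome; one sentence differs. This stands. The listing needs correcting, but it is weak evidence that the outcome's status was deliberately left open.
- **If all three primaries had to succeed, no adjustment would be needed.** That is correct in principle, but the plan does not state such a rule, and a claim on BOP alone would not meet it.
- **The test count can be exaggerated.** A reader might count 27 tests (3 outcomes × 3 pairs of arms × 3 visits) and infer 1 − 0.95²⁷ = 75%. The documents do not support this. Pairwise contrasts share arms and cannot be independent: simulation of those 27 tests gave 38–68%. The plan does not specify pairwise tests at each visit, and it states visit-by-visit comparison only for PD and CAL.
- **BOP is not the only outcome with a positive statement.** The Abstract and Conclusion also report significant improvement in pocket depth and attachment level, within the gel arms. BOP is the outcome on which the Discussion claims an effect of the regimen, but it is not the only significance reported.

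A reader might also infer that multiplicity produced the BOP claim. The text does not show that: the claim fails first because no between-group comparison is reported, and a stricter threshold would not repair that.

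**Conclusion.** The concern holds at moderate size. The plan has no rule that turns three primary outcomes into one conclusion at 5%. On the three null hypotheses that it states, tested once each at one visit, the false-positive chance is about 10–14%, roughly two to three times the nominal level. The 20–37% range applies only if visit-by-visit testing is extended to BOP as well.

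Both ranges assume no true differences, normally distributed per-patient means, and correlations that the documents do not supply. Only the 14.3% (independence) and the 15% ceiling are free of assumed correlations. Within-arm tests would add to the total. The BOP statement in the Discussion is unsupported on two separate grounds: it has no controlled error rate, and no between-group test is shown.

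**What to change.** 1. Remove BOP from the secondary list.
2. For primary objective 1, name the between-group comparison of PD, RAL and BOP at week 26 as decisive, and test the three under Holm (0.0167, 0.025, 0.05). A significant three-group test does not itself show that gel differs from SRP, so contrasts of each gel arm with SRP should follow only for outcomes that pass. Pooling the gel arms is not needed and would be debatable, since HP13 stops gel at week 13.
3. Give primary objective 2 (week 4, before SRP) a named outcome and its own place: either after objective 1 in a fixed order, or with a share of the 0.05. A share lowers the Holm thresholds. For example, 0.01 for objective 2 leaves 0.04, and the first threshold becomes 0.04/3 = 0.0133.
4. Reconcile the visit descriptions first. The Abstract counts weeks from SRP, whereas the Study Schedule counts from baseline. The schedule for the SRP arm lists no week-4 measurements, although the Results report them.
5. Test HP13 against HP26 afterwards, as the stated secondary objective.
6. Report other visits and within-arm changes with confidence intervals and no significance claim.
7. Label this re-analysis post hoc, because results are already reported. Withdraw or qualify the Discussion's BOP claim unless a between-group BOP test supports it.

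The cost is mostly wording, one re-analysis, and a stricter threshold for the primary outcomes. With 3, 3 and 9 completers, that stricter threshold will be hard to meet.
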